9.4.5 Baseline Descriptive Statistics

A summary table with descriptive statistics will be generated for baseline characteristics, including demographics and laboratory measurements based on the ITT population. Baseline characteristics will be presented by intervention groups in a table, but no formal statistical hypothesis testing will be performed. Continuous variables will be summarized using mean with standard deviation or median with interquartile range. Categorical variables will be summarized using frequency and percentage.

Baseline characteristics include demographics, medical history, surgical history, physical exam, pelvic ultrasound, MR defecography, POPQ, PFDI, Pain Scale, Assessment of pain medication use, and Activity assessment scale.

9.4.6 Planned Interim Analysis

No interim analyses are planned.

9.4.7 Sub-Group Analyses

Subgroup analyses of the primary efficacy endpoint will be conducted for demographics (e.g., age, BMI, menopausal status, parity), duration and severity of ODS, and concomitant surgery. Descriptive statistics will be presented stratified by aforementioned variables. Data will be analyzed using the same method as described for the primary efficacy endpoint.

9.4.8 Tabulation of Individual Participant Data

Not Applicable

9.4.9 Exploratory Analyses

We will investigate the correlation between measurements of compression ratio between two modalities and present a cut-off for these measurements relevant to presence of OD symptoms in our secondary endpoints. For an optimal cut-off, the sensitivity and specificity will be calculated based on receiver operating characteristic (ROC) curve.

We will develop and validate a computational finite element model and statistical shape modeling approach to describe the mechanics of normal defecation and the role of rectal and vaginal support deficiencies in causing OD symptoms.

10. Supporting Documentation and Operational Considerations

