It is worth emphasizing that along with the strong and robust correlations observed between OD symptoms and US-detected rectal hypermobility, our findings indicated a clear lack of correlation between OD symptoms and the presence or absence of rectocele as diagnosed via pelvic examination. While posterior vaginal compartment prolapses (i.e. rectoceles) may certainly account for bothersome symptoms including vaginal bulging and laxity, rectoceles appear to have essentially no relationship to obstructive defecation which was related to only one anatomic finding: excessive mobility of the rectum that is usually occult and easily detected by ultrasound. This core observation would, arguably, make it unsurprising that rectocele repairs have performed poorly to resolve obstructive defecation symptoms (24, 25). Furthermore, this diagnostic/anatomic finding provided the basis for our proposed surgical approach, transvaginal sacrospinous rectopexy.

OD symptoms persist after conventional vaginal prolapse repairs at 2 years follow up (5)

The previous finding regarding the role of POP was further demonstrated when we performed a sub-analysis of two major clinical trials performed by the Pelvic Floor Disorders Network: the Colpopexy and Urinary Reduction Efforts (CARE) trial and the Operations and Pelvic Muscle Training in the Management of Apical Support Loss (OPTIMAL) trial (55, 56). The study aimed to address 2 questions: 1) is any conventional vaginal prolapse repair effective in curing OD symptoms, and 2) is there evidence to suggest that a sacrocolpopexy will increase the risk of worsening or newly onset OD symptoms?

Regardless of trial, OD symptoms were present in more than half of the patients at the initial visit before the surgical intervention and interestingly about one third of the patients were symptomatic at the 24-month follow-up interval in all conventional vaginal prolapse surgeries, with or without posterior vaginal wall repair (353 participants from OPTIMAL and 279 participants from CARE). It is also important to note that about 1/4 of the patients experienced worsening of their OD symptoms in the absence of anatomical failure. These data further support our overall hypothesis for this proposal that OD symptoms primarily result from structural defects in rectal support and not as a result of a loss in vaginal support, challenging the current standard for surgical treatment.

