This was a prospective case series study performed during December 2018-July 2020 and aimed to investigate the safety, efficiency, and durability of transvaginal sacrospinous rectopexy in women with OD symptoms and significant rectal hypermobility/folding (15). 20 patients underwent the procedure and completed the follow up at 2 and 12 months postoperatively. Statistically significant improvements were observed in all OD symptoms and subjective improvement ($94.7\% \pm 13.4$ and $90.6\% \pm 18$) at 2 and 12 months after the surgery, respectively. Mean rectal compression ratio, detected via ultrasound, improved from $45.5\% \pm 18.4$ preoperatively to $9.2\% \pm 13.7$ at 2 months ($p <0.0001$) and $19.6\% \pm 14.4$ at 12 months ($p<0.0012$). Surgical failure, defined as combined subjective (OD symptoms $> 50\%$ of bowel movements) and anatomical failure (rectal compression ratio $>25\%$), occurred in two patients. Overall, this study demonstrated that transvaginal sacrospinous rectopexy was safe, feasible, and effectively treated OD symptoms within this cohort of women undergoing POP surgery with rectal hypermobility confirmed by dynamic ultrasound.

The proposed Latin hypercube parametric study based on finite element analysis and statistical shape modeling was successful in identifying the relative contributions of urethral support (53, 54)

In a recent set of publications (53, 54), we utilized the finite element method and statistical shape modeling to elucidate the role of supportive tissues on the urethra during Valsalva. While these papers focused on the urethra, the methods and workflow will be similar to that utilized by this proposal. A finite element model of the urethra and its supports was created (Figure 3).

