5.1 Inclusion Criteria

In order to be eligible to participate in this study, an individual must meet all of the following criteria:

1. Female, between the age of 18 and 80
2. OD symptoms as indicated by an affirmative response to either questions 7, 8 or 14 of the Pelvic Floor Distress Inventory (PFDI):
 - a. Do you feel you need to strain too hard to have a bowel movement?
 - b. Do you feel you have not completely emptied your bowels at the end of a bowel movement?
 - c. Does part of your bowel ever pass through the rectum and bulge outside during or after a bowel movement?
3. Rectal hypermobility defined as a compression ratio greater than 50% according to ultrasound
4. Patient planning on undergoing surgery for the repair of pelvic organ prolapse within the next 12 months
5. Patient who is not pregnant and does not intend to become pregnant in the next 2 years
6. Available for 24-months of follow-up
7. Stated willingness to comply with all study procedures and availability for the duration of the study
8. Able to complete study assessments, per clinician judgment
9. Able and willing to provide independent written informed consent

10. Stable cardiovascular and respiratory status to meet candidacy in vaginal or laparoscopic surgeries

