9.2 Sample Size Determination

Based on our preliminary studies in literature (83-87), we assume an anatomic success rate in LAVR group is about 70% at 24 months. The investigators believe that a difference in success rates less than 25% will not change clinical practice, but also that the sample size should be large enough so that an observed difference in success rates of 20% would be significant; i.e., an inability to differentiate between the procedures will require an observed difference that is less than 20%.

The study will be individually randomized group-treatment trial (IRGT), which patients are randomized to surgical interventions through a common surgeon (88-90). There will be three surgeons performing each surgical treatment. The number of surgeons and patients will be the same in each clinical site. We anticipate an average of 16 individually randomized patients per surgeon in each treatment group. Outcomes for patients treated by the same surgeon tend to be more similar. We assume minimal variability, estimating a small intraclass correlation coefficient (ICC) of 0.01. The table below illustrates power to detect at least 23% difference between treatment groups with varying assumptions on ICC and dropout rates. A total of 96 patients (48 patients per group) would yield 86% power to differentiate between anatomical success rates of 70% and 93% assuming an ICC of 0.01 and a two-sided 5% level of significance. Projecting a 20% dropout/loss to follow up rate over 2 years, we anticipate recruiting and up to 120 total patients.

ICC	% Dropout	Total patients	Average patients per surgeon	Power
0.01	0	120	20	92%
	10	108	18	90%
	20	96	16	86%
0.02	0	120	20	90%
	10	108	18	87%
	20	96	16	83%
0.05	0	120	20	82%
	10	108	18	79%
	20	96	16	76%

Due to concerns that ICC is higher than expected or dropout rate is higher than 20% toward the end of 2-year follow-up, we calculated the sample size that would be needed for 87% power to differentiate between anatomical success rates of 70% and 95% (a difference of 25%) in treatment groups with a two-sided 5% level of significance. The required sample size is 39 per group, or 78 total patients.

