9.4.3 Analysis of the Secondary Endpoint(s)

Subjective Surgical Outcome

The secondary endpoint is the presence of OD symptoms (yes/no) at 24 months after surgery. Questionnaires that assess the presence and severity of OD symptoms include pain/activity assessment scale, global improvement in bladder function, prolapse and colorectal symptoms as assessed by POPDI, CRADI, UDI, quality of life by PFIQ, SF-36, EQ-5D, and pelvic muscle strength measured by Brink Scale. Differences between surgical treatments will be analyzed using generalized linear mixed-effects models, as described for the primary endpoint. However, imputation of missing values will not be done for secondary measures.

Validation

There will be two forms of validation: statistical and radiological. For statistical validation, we expect to see a significant and positive correlation between measurements of the Compression ratio between the two modalities. However, since the Compression ratio as measured via MR defecography is not used clinically to diagnose abnormalities in rectal support (rectal prolapse or rectal intussusception), this does not validate the use of ultrasound for diagnostic purposes. Thus, radiological validation will be performed where the Compression ratio is also correlated with a radiologist's diagnosis of an abnormality in rectal support.

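### Exploratory ROC analysis: accuracy at a data-chosen compression-ratio cut-off is read from the women who chose it, with no correction planned, so on average it will be overstated

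*Combined protocol and SAP*

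**What the plan says.** Section 9.4.9 (Exploratory Analyses) will correlate compression ratio between ultrasound and MR defecography and "present a cut-off for these measurements relevant to presence of OD symptoms in our secondary endpoints". It continues: "For an optimal cut-off, the sensitivity and specificity will be calculated based on receiver operating characteristic (ROC) curve". The secondary endpoint it points to is in section 9.4.3: "The secondary endpoint is the presence of OD symptoms (yes/no) at 24 months after surgery".

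The plan does not say what makes a cut-off optimal. It describes no second sample, cross-validation, bootstrap or confidence interval for these figures. The validation paragraph in 9.4.3 concerns correlation between the two modalities and with a radiologist's diagnosis; it does not test the accuracy of the chosen cut-off. Section 9.4.1 leaves implementation to a SAP to be written before database lock.

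The protocol already holds fixed compression-ratio thresholds. Section 4.2 splits women at 14 when relating the ratio to OD symptoms, and sections 3 and 8.1 use 20% for surgical failure.

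**The concern.** The cut-off that looks best in a sample owes its place partly to the true separation between groups and partly to chance. If sensitivity and specificity are read from the same sample, the chance part is counted as accuracy. The bias grows as the smaller group shrinks, and here the smaller group may be very small.

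The analysis can only use post-operative data, since every woman has OD symptoms at entry ("OD symptoms as indicated by an affirmative response to either questions 7, 8 or 14", section 5.1) and specificity needs women without them. The Schedule of Activities places MR defecography before surgery only, so the concern applies to the ultrasound ratio at 24 months.

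At stake are the accuracy figures and the cut-off that readers would take from the trial, in a setting where comparing ultrasound with MR defecography is a listed secondary outcome.

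**Working it through.** **Plan's own figure.** Section 9.4.9 gives none (no N, accuracy target or interval), so there is nothing to reproduce.

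**Inputs.**
- Women at 24 months: 96, from section 9.2 ("A total of 96 patients (48 patients per group) would yield 86% power"; "Projecting a 20% dropout/loss to follow up rate over 2 years, we anticipate recruiting and up to 120 total patients"). Check: 120 × (1 − 0.20) = 96.
- OD prevalence at 24 months: not given, so a range is assumed. In section 4.2, "about one third of the patients were symptomatic at the 24-month follow-up interval" after conventional prolapse surgery: 96 / 3 = 32 women. In the transvaginal case series, combined subjective and anatomical failure "occurred in two patients" of 20, or 10%: 0.10 × 96 ≈ 10 women. Neither is an estimate of OD presence in this trial. Because any one of three PFDI items counts as OD at entry, 50% (48 women) is included as well.
- True AUC: not given; 0.6 to 0.9 assumed.
- Cut-off rule: not given; the maximum of the Youden index is assumed.

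**Model.** The marker is N(0,1) without OD and N(μ,1) with OD, where μ = √2 · Φ⁻¹(AUC). In each of 4,000 simulated trials per setting, the cut-off ĉ maximises the sample value of J = sensitivity + specificity − 1. The true value at that same cut-off is J(ĉ) = Φ(ĉ) − Φ(ĉ − μ). Optimism is the mean of apparent J minus true J(ĉ).

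**Results, N = 96** (percentage points of sensitivity plus specificity):

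| Women with OD | Optimism as AUC falls from 0.9 to 0.6 |
|---|---|
| 10 | 12.5 to 18.3 |
| 32 | 7.4 to 11.7 |
| 48 | 6.7 to 10.9 |

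For AUC 0.65-0.85, optimism is about 14-18 points at 10% positive, 10-13 at 20% and 8-11 at one third. With all 120 women retained, the range over AUC 0.6-0.9 is 6.0 to 16.8.

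**Split between the two measures, AUC 0.8.**
- 32 with OD: sensitivity 78.1% apparent against 72.2% true (5.9 points); specificity 73.4% against 70.5% (2.9 points). Total 8.8; share in sensitivity 5.9 / 8.8 = 67%.
- 10 with OD: sensitivity 81.8% against 68.2% (13.6 points); specificity 74.7% against 73.0% (1.7 points). Total 15.3.

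**How often.** Apparent J exceeded true J in 83% to 97% of simulated trials, depending on the setting.

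**Precision of the cut-off.** At one third positive and AUC 0.65-0.85, the 5th-95th percentile range of ĉ spans 1.0 to 1.6 within-group SDs.

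**Does the remedy work?** Mean J over 300 trials per setting, with 100 bootstrap resamples that each re-select the cut-off (N = 96):

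| Setting | Apparent | Corrected | True | Bias removed |
|---|---|---|---|---|
| AUC 0.8, 32 with OD | 0.512 | 0.451 | 0.427 | 0.061 / 0.085 = 72% |
| AUC 0.8, 10 with OD | 0.553 | 0.463 | 0.415 | 0.090 / 0.138 = 65% |
| AUC 0.7, 32 with OD | 0.371 | 0.302 | 0.267 | 0.069 / 0.104 = 66% |

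A cut-off fixed in advance showed essentially no optimism: at AUC 0.8, apparent J was 0.444 (32 with OD) and 0.450 (10 with OD) against a true 0.448.

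**The case against.** The analysis is brief, labelled exploratory, touches neither the primary test nor the sample size, and is open to completion in the later SAP. All of that stands and limits the weight of the point. It does not remove the bias, because nothing now commits the SAP to a correction.

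That the same women choose and score the cut-off is inferred: one cohort is described and no correction is mentioned, but the text does not say so outright. The Youden rule, AUC and prevalence are also assumed. They set the size of the bias; its direction on average held in every setting tried.

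Three stronger readings are tempting, and the documents do not support them.
- A reader might infer that the published accuracy is certain to be too high. In 3% to 17% of simulated trials it was not; the claim is about the average.
- A reader might infer that the trial sets out to establish ultrasound as the diagnostic test for OD, and that a flawed cut-off would pass into practice. The stated outcome is a comparison of ultrasound with MR defecography, and 9.4.3 itself says that correlation between modalities does not validate ultrasound for diagnosis.
- A reader might turn the cut-off's spread into compression-ratio points using the case-series SD of 14.4. That SD is from 12 months, from transvaginal surgery only, and from all 20 patients together, whereas the simulated spread is in within-group SDs at 24 months over both arms. The conversion is not sound.

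The headline range is also a sum of two measures; neither sensitivity nor specificity alone is overstated by the full amount.

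**Conclusion.** The point holds as a statement of average bias in an exploratory analysis. Followed as written, 9.4.9 will on average overstate sensitivity plus specificity by about 7-18 points, given a Youden-type rule, about 96 women, 10-50% with OD and AUC 0.65-0.90. At the one-third anchor the figure is about 8-11 points, and sensitivity carries roughly two thirds of it. With few OD-positive women, nearly all of the bias falls on sensitivity. The selected cut-off will be imprecise. The primary comparison is untouched. The point is worth acting on because the remedy is cheap and the SAP is still to be written.

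**What to change.** In section 9.4.9 or the SAP:

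1. Name the rule that defines the optimal cut-off, and state the visit and the women used.
2. Lead with the AUC and its confidence interval.
3. Report sensitivity and specificity, with confidence intervals, at thresholds the protocol already contains: 14 (related to OD in section 4.2) and 20% (surgical failure, sections 3 and 8.1). Neither needs a search in the trial data. State what each was set for, since the 20% threshold was not set for OD.
4. For any data-chosen cut-off, report accuracy corrected by a bootstrap or cross-validation that repeats the choice of cut-off in each resample, and give a confidence interval for the cut-off itself.
5. Say that the correction is partial; in the check above the bootstrap removed about two thirds of the bias. This is why items 2 and 3 should lead.

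Cost: a few lines of code and a slightly less favourable stated accuracy. Visits, sample size and trial conduct do not change.

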10.1 Regulatory, Ethical, and Study Oversight Considerations

10.1.1 Informed Consent Process

10.1.1.1 Consent and Other Informational Documents Provided to Participants

Consent forms describing in detail the study intervention, study procedures, and risks are given to the participant and written documentation of informed consent is required prior to starting intervention/administering study intervention. The risks and benefits of each surgical approach including the risk of prolapse recurrences will be discussed during consent and pre-operative visits. During the pre-operative visit, which will occur after anesthesiologist clearance and randomization, participants will have the opportunity to review the surgery details with the surgeon. Participants randomized to laparoscopic ventral rectopexy will complete the preoperative visit with a colorectal surgeon. Those assigned to transvaginal sacrospinous rectopexy will complete the preoperative visit with a urogynecologist. Every effort will be made to minimize the time between randomization and the surgery. Surgical failure resulting from either surgical approach will be addressed per current guidelines for surgical failures which include symptoms assessment for conservative or surgical management.

10.1.1.2 Consent Procedures and Documentation

Informed consent is a process that is initiated prior to the individual's agreeing to participate in the study and continues throughout the individual's study participation. Consent forms will be Institutional Review Board (IRB)-approved and the participant will be asked to read and review the document. Written informed consent will be obtained from all study participants. Consent will be obtained by study-related personnel who are knowledgeable of the study and who have training in the consent process and in the protection of human participants. No study-related procedures (interview, chart abstraction, research ultrasound studies, questionnaires) will be undertaken before a signed consent form has been completed. During the process of obtaining informed consent, potential participants will have the nature of the study, specimen collection, data collection procedures, study ultrasound procedures, the importance of compliance to study procedures, and the potential risks and benefits explained to them. Potential participants will be told that there is no obligation to participate, that there will be no penalty for declining to participate and that their treatment will not be compromised if they choose not to participate or cease participation at any time. Ample time will be provided for each potential participant to read and understand the consent form and to ask questions. The potential participant will be able to take the consent form/informational form home to discuss participation with family/friends/personal physician. A separate visit will be scheduled for the potential participant to return to the clinic to ask questions and sign the consent form with the research coordinator or research assistant. A participant who consents to the study will be given a copy of the signed consent form for their personal records. A copy will be placed in their medical record. The original signed copy will be kept in a locked file at the clinical site with other confidential information on the participant.

10.1.2 Study Discontinuation and Closure

This study may be temporarily suspended or prematurely terminated if there is sufficient reasonable cause. Written notification, documenting the reason for study suspension or termination, will be provided by the suspending or terminating party to study participants, investigator, funding agency, and regulatory authorities. If the study is prematurely terminated or suspended, the Principal Investigator (PI) will promptly inform study participants, the Institutional Review Board (IRB), and sponsor and will provide the reason(s) for the termination or suspension. Study participants will be contacted, as applicable, and be informed of changes to study visit schedule.

Circumstances that may warrant termination or suspension include, but are not limited to:

- Determination of unexpected, significant, or unacceptable risk to participants
- Demonstration of efficacy that would warrant stopping
- Insufficient compliance to protocol requirements
- Data that are not sufficiently complete and/or evaluable
- Determination that the primary endpoint has been met
- Determination of futility

Study may resume once concerns about safety, protocol compliance, and data quality are addressed, and satisfy the sponsor and IRB.

